6.18.5.3. Lipid Effects

Lipid effects will be assessed through analysis of elevated total cholesterol, elevated low-density lipoprotein (LDL) cholesterol, decreased and increased high-density lipoprotein (HDL) cholesterol, and elevated triglycerides. The planned summaries are provided in [Table JAHV.6.17](#) and are described more fully in compound-level safety standards.

Table JAHV.6.17. Summary Tables Related to Lipid Effects

Analysis
Shift tables showing the number and percentage of patients based on baseline to maximum will be created, with baseline depicted by the most extreme NCEP-based level during the baseline period. With each shift table, a summary displaying the number and percentage of patients who decreased, increased, or stayed the same in NCEP-based level will be presented.
The number and percentages of patients with treatment-emergent shifts at any time will be summarized, based on increases to various levels of NCEP-based categories.
The number and percentages of patients with treatment-emergent potential hyperlipidemia will be summarized using a predefined MedDRA list of PTs that is a subset of the narrow scope PTs in the MedDRA SMQ “Dyslipidemia” (code 200000026) (see compound-level safety standards)..

Abbreviations: MedDRA = Medical Dictionary for Regulatory Activities; NCEP = National Cholesterol Education Program; PT = Preferred Term; SMQ = Standardised MedDRA Query.

Categorical analyses will be performed using Expert Panel on Integrated Guidelines for Cardiovascular Health and Risk Reduction in Children and Adolescents (2011) as shown in the [Table JAHV.6.18](#).

Table JAHV.6.18. Acceptable, Borderline-High, and High Plasma Lipid, Lipoprotein, and Apolipoprotein Concentrations for Children and Adolescents

Category	Low (mg per dL) ^a	Acceptable (mg per dL)	Borderline-high (mg per dL) ^a	High (mg per dL) ^a
total cholesterol	--	<170	170 to 199	≥200
LDL cholesterol		<110	110 to 129	≥130
Non-HDL cholesterol		<120	120 to 144	≥145
Apolipoprotein B		<90	90 to 109	≥110
Triglycerides				
0 to 9 years of age		<75	75 to 99	≥100
10 to 19 years of age		<90	90 to 129	≥130
HDL Cholesterol	<40	>45	40 to 45	
Apolipoprotein A-1	<115	>120	120	

Abbreviations: HDL= high-density lipoprotein; LDL= Low-density lipoprotein

^a Low cut point for HDL cholesterol and apolipoprotein A-1 represent approximately the 10th percentile. The cut points for high and borderline-high represent approximately the 95th and 75th percentiles, respectively.

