- u Pregnancy tests prior to first dose of investigational product for females ≥ 10 years old of age (< 10 years at investigator discretion) if menarche reached or if there is reason to believe the patient is sexually active. Pregnancy test results from Visit 5 must be known prior to first dose of investigational product.
- v Clinical chemistry will include eGFR (calculated by Bedside Schwartz 2009 formula or the Japanese Society for Pediatric Nephrology formula for patients in Japan).
- w Fasting lipid profile: Patients should not eat or drink anything except water for 4-12 hours depending on weight and age as specified below. If a patient attends these visits in a nonfasting state, this will not be considered a protocol violation. Recommended fasting times by age and weight are as follows:
- Patients ≥ 12 years: fast for 12 hours prior to laboratory test
 - Patients 8 to < 12 years and weighing > 50 kg: fast for 12 hours prior to laboratory test
 - Patients 8 to < 12 years and weighing ≤ 50 kg: fast for 8 hours prior to laboratory test
 - Children < 8 years and weighing 25 to ≤ 50 kg: fast for 8 hours prior to laboratory test
 - Children < 8 years and weighing 10 to < 25 kg: fast for 6 hours prior to laboratory test
 - Children < 8 years and weighing < 10 kg: fast for 4 hours prior to laboratory test
- x Patients in the age cohort of age 2 to ≤ 7 years will not have flow cytometry testing due to blood volume limitations.
- y If patients are eligible for vaccination with tetanus, diphtheria, and pertussis (tDaP) and/or pneumococcal conjugate vaccine according to local recommended schedule of vaccination, IgG titers for eligible vaccine will be evaluated at pre-vaccination, 4 weeks post vaccination, and 12 weeks post vaccination.
- z Estradiol (for females) or testosterone (for males) will be collected for the assessment of pubertal development in patients aged 8 to < 18 years.
- aa PK samples will be collected as described in Sections 9.5.2 and 9.5.3.
- NOTE: Due to blood volume restrictions, some laboratory tests may not be collected. Laboratory samples are recommended to be collected as described in the sponsor-provided weight-based prioritization chart in [Appendix 6](#).

3. Introduction

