Abbreviations: ACPA = anti-citrullinated protein antibodies; ALP = alkaline phosphatase; ALT = alanine aminotransferase; AST = aspartate aminotransferase; BUN = blood urea nitrogen; CPK = creatine phosphokinase; DNA = deoxyribonucleic acid; eGFR = estimated glomerular filtration rate; ESR = erythrocyte sedimentation rate; hBcAb = hepatitis B core antibody; hBsAb = hepatitis B surface antibody; hBsAg = hepatitis B surface antigen; HBV = hepatitis B virus; HIV = human immunodeficiency virus; hsCRP = high sensitivity C-reactive protein; IgA = immunoglobulin A; IgG = immunoglobulin G; IgM = immunoglobulin M; IGF-1 = insulin-like growth factor-1; IGFBP-3 = insulin-like growth factor-binding protein-3; NK = natural killer; OLLI = open-label lead-in; PK = pharmacokinetic; PPD = purified protein derivative; RBC = red blood cell; RNA = ribonucleic acid; TB = tuberculosis; TIBC = total iron-binding capacity; TSH = thyroid-stimulating hormone; WBC = white blood cell.

- a. Unscheduled or repeat blood chemistry, hematology, and urinalysis panels may be performed at the discretion of the investigator, as needed.
- b. Fasting laboratory values for glucose and lipids will be required at baseline and Week 12 of OLLI. Patients should not eat or drink anything except water for 4-12 hours depending on weight and age as specified below. If a patient attends these visits in a nonfasting state, this will not be considered a protocol violation. Recommended fasting times by age and weight are as follows:
 - Patients ≥ 12 years: fast for 12 hours prior to laboratory test
 - Patients 8 to <12 years and weighing >50 kg: fast for 12 hours prior to laboratory test
 - Patients 8 to <12 years and weighing ≤ 50 kg: fast for 8 hours prior to laboratory test
 - Children <8 years and weighing 25 to ≤ 50 kg: fast for 8 hours prior to laboratory test
 - Children <8 years and weighing 10 to <25 kg: fast for 6 hours prior to laboratory test
 - Children <8 years and weighing <10 kg: fast for 4 hours prior to laboratory test

These tests may be performed in a nonfasting state at all other visits.

- c. eGFR calculated by Bedside Schwartz 2009 formula or the Japanese Society for Pediatric Nephrology formula for patients in Japan.
- d. Microscopic examination of sediment performed only if abnormalities are noted on the routine urinalysis.
- e. Test required at Visit 1 only to determine eligibility of patient for the study.

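### SAP 6.18.5.3 promises to assess decreased HDL, but its lipid tables are built for elevations and leave the HDL ordering wrong or undefined

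*SAP*

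**What the plan says.** SAP 6.18.5.3 lists among the lipid effects to be assessed "decreased and increased high-density lipoprotein (HDL) cholesterol, and elevated triglycerides". Table JAHV.6.17 then gives three analyses:

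- Row 1: "Shift tables showing the number and percentage of patients based on baseline to maximum will be created". Baseline is the most extreme level in the baseline period. Each shift table comes with "a summary displaying the number and percentage of patients who decreased, increased, or stayed the same in NCEP-based level will be presented".
- Row 2: treatment-emergent shifts at any time, "based on increases to various levels of NCEP-based categories".
- Row 3: a list of adverse event terms for hyperlipidemia.

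The levels come from Table JAHV.6.18. For HDL these are Low (<40 mg/dL), Acceptable (>45 mg/dL), and 40 to 45 mg/dL, which is printed in the Borderline-high column. There is no High level for HDL. The table's footnote says: "Low cut point for HDL cholesterol and apolipoprotein A-1 represent approximately the 10th percentile". It puts the borderline-high cut at about the 75th percentile.

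On sampling, the schedule in protocol Table JAHV.2 labels its lipid row as fasting, and footnote w reads: "Fasting lipid profile: Patients should not eat or drink anything except water for 4-12 hours depending on weight and age". Protocol Appendix 2, footnote b, requires fasting lipids and glucose at baseline and Week 12, and then says: "These tests may be performed in a nonfasting state at all other visits".

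**The concern.** For total cholesterol, LDL and triglycerides the adverse direction is up, and the rules in Table JAHV.6.17 suit them. For HDL the only abnormal category the SAP names is Low, so the adverse direction is down. Maximum values and category increases look at the wrong end.

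If the rules are programmed as written, the pediatric lipid tables can under-count children whose HDL becomes low and can count a partial recovery as a treatment-emergent shift. Lipid monitoring is a named part of the cardiovascular monitoring plan in protocol 9.4.6, so readers are likely to rely on these tables. Two programmers could also order the HDL levels differently and produce different counts from the same data.

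**Working it through.** The plan states no figure on this point, so there is none to reproduce. The check applies the rules of Table JAHV.6.17 to the HDL levels of Table JAHV.6.18. The patient values are illustrative assumptions.

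**Possible orderings of the three HDL levels, lowest to highest**

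- By concentration: <40, then 40-45, then >45.
- By printed column: Low (<40), then Acceptable (>45), then Borderline-high (40-45).
- By severity: >45, then 40-45, then <40.

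**Results.** The first entry is the row 1 classification, using the highest postbaseline level. The second says whether row 2 counts a treatment-emergent increase.

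| Baseline → postbaseline (mg/dL) | By concentration | By printed column | By severity |
|---|---|---|---|
| 50 → 38, 42, 50 | same; no | increased; yes | increased; yes |
| 50 → 38, 36, 39 | decreased; no | decreased; no | increased; yes |
| 50 → 42 | decreased; no | increased; yes | increased; yes |
| 38 → 42 | increased; yes | increased; yes | decreased; no |

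**What follows**

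1. By concentration, row 1 uses the largest postbaseline value. A child with an acceptable baseline is counted as decreased only if every postbaseline value is 45 or below, and is shown as Low only if every one is below 40. In the first case the maximum is 50, so the value of 38 leaves no trace. In the second the maximum is 39, so the fall is captured.
2. By concentration, row 2 never counts a fall, however deep or sustained. It does count the rise from 38 to 42.
3. By printed column, row 2 counts 50 to 42 but not a fall in which every value is below 40. A mild fall is flagged and a deeper one is not.
4. Only the severity ordering gives a valid count of adverse HDL shifts. The SAP does not state that ordering.
5. The footnote to Table JAHV.6.18 does not support the column placement. The 40-45 band starts at the low cut, which the footnote puts near the 10th percentile, whereas it puts the borderline-high cut near the 75th.

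**Fasting.** Appendix 2 permits nonfasting samples at every visit other than baseline and Week 12. Table JAHV.2 labels the whole lipid row as fasting. The exact marked visits cannot be read reliably from the text available, but Week 44 appears to be one of them, and one marked visit after Week 12 is enough for the two statements to differ.

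**The case against.** A reader might infer that the lipid tables track only increases, that every HDL decrease is invisible, and that the stated aim therefore cannot be met. The documents do not support this, for three reasons.

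- The summary attached to row 1 counts patients who decreased. A child who goes from 55 to 35 mg/dL and stays there is captured; that child is missed by row 1 only if another postbaseline value remains above 45.
- Other analyses look downward. Table JAHV.6.12 tabulates shifts to low and shows change from baseline. SAP 6.1.4 adds treatment-emergent high and low results, and an ANCOVA of laboratory variables, in the double-blind period.
- SAP 6.18.5.3 defers detail to compound-level safety standards that are not part of these documents and may settle the ordering.

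It can also be said that maximum means worst. Table JAHV.6.16 uses the same template sentence for blood counts, where a low count carries a higher CTCAE grade.

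The first two points stand and limit the claim. They do not close the gap. Neither Table JAHV.6.12 nor 6.1.4 is specified at the <40 mg/dL pediatric cut, and ANCOVA describes a mean change rather than how many children become low. The worst-category reading is possible, but CTCAE grades are severity grades by construction, whereas the HDL levels are concentration bands with no stated severity order. The unseen standards might help, but Table JAHV.6.18 is this SAP's own pediatric table and is where its ordering should be clear.

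Nor do the documents show that an HDL rise would be reported as harm. The SAP plans to look at increased HDL too, and Table JAHV.6.17 does not label any shift adverse.

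**Conclusion.** The point holds for HDL in rows 1 and 2 of Table JAHV.6.17 and for the HDL line of Table JAHV.6.18. As specified, the lipid-specific tables do not give a sound count of children whose HDL falls to the pediatric low range: row 1 misses transient falls, row 2 misses all falls, and the middle band is mislabelled. This rests on reading the levels by concentration, or as printed; it would fall away if a severity ordering were stated. The documents give no HDL distribution, so the number of children affected cannot be estimated. The display is descriptive, other analyses give partial cover, and the primary analysis is untouched.

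The fasting mismatch is real but minor. Footnote w presents its fasting times as recommendations and does not treat nonfasting attendance as a violation. A reader might infer that nonfasting samples will inflate high-triglyceride counts in both arms and dilute the treatment contrast, or that triglyceride and glucose category tables should be limited to fasting samples. The documents give no figure for the first. For the second, no passage cited here shows that fasting status is recorded, and SAP 6.18.5.3 has no glucose category table. This part supports only reconciling the passages.

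**What to change.** In Table JAHV.6.17, give HDL its own rule: baseline-to-minimum shifts, and treatment-emergent decreases to 40-45 mg/dL and to <40 mg/dL. State the order of the HDL levels, and say that the most extreme baseline level for HDL is the lowest. In Table JAHV.6.18, relabel the 40-45 band as borderline-low. If rises in HDL are also to be shown, keep baseline-to-maximum as a second, separately labelled display.

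The cost is a few lines of SAP text and the programming of one analyte. No new data are needed. If the compound-level standards already define the HDL direction, a sentence citing that definition, together with the relabelling, would be enough.

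Separately, protocol Appendix 2 footnote b and the lipid row of Table JAHV.2 with footnote w must be reconciled so that sites have one statement of the fasting state intended at each lipid visit. This is a wording change.

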6.18.5.4. Renal Function Effects

Effects on renal function will be assessed through analysis of elevated creatinine. The planned summaries are provided in [Table JAHV.6.19](#) and are described more fully in compound-level safety standards.

Table JAHV.6.19. Summary Tables Related to Effects on Renal Function

Analysis
Shift tables showing the number and percentage of patients based on baseline to maximum will be created, with baseline depicted by the most extreme CTCAE grade during the baseline period. With each shift table, a summary displaying the number and percentage of patients who decreased, increased, or stayed the same in CTCAE grade category will be presented.
The number and percentages of patients with treatment-emergent shifts at any will be summarized, based on any increase to CTCAE Grade 1 or above, Grade 2 or above, Grade 3 or above, and Grade 4 or above.

Abbreviations: CTCAE = Common Terminology Criteria for Adverse Events.

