- [41] Patients who are receiving thyroxine as replacement therapy may participate in the study, provided stable therapy has been administered for ≥ 12 weeks and thyroid-stimulating hormone (TSH) is within the laboratory's reference range.

Exception: Patients who are receiving stable thyroxine replacement therapy who have TSH marginally outside the laboratory's normal reference range may participate if the treating physician has documented that the thyroxine replacement therapy is adequate for the patient.

Diagnostic Assessments

[42] Have any of the following specific abnormalities on screening laboratory tests:

- AST or ALT ≥ 2 x upper limit of normal (ULN)
- Total bilirubin level (TBL) ≥ 1.5 x ULN
- Alkaline phosphatase (ALP) ≥ 2 x ULN
- Hemoglobin < 10.0 g/dL (100.0 g/L)
- Total white blood cell count < 3000 cells/ μ L ($< 3.00 \times 10^3$ / μ L or < 3.00 billion/L)
- Neutropenia (absolute neutrophil count [ANC] < 1500 cells/ μ L) ($< 1.50 \times 10^3$ / μ L or < 1.50 billion/L)
- Lymphopenia (lymphocyte count < 1000 cells/ μ L) ($< 1.00 \times 10^3$ / μ L or < 1.00 billion/L)
- Thrombocytopenia (platelets $< 100,000$ / μ L) ($< 100 \times 10^3$ / μ L or < 100 billion/L)
- eGFR < 40 mL/min/1.73 m² are excluded from enrolling in the study (Bedside Schwartz formula 2009 or The Japanese Society for Pediatric Nephrology formula for patients in Japan)
- eGFR < 60 mL/min/1.73 m² are excluded from the Safety/PK period of the study (Bedside Schwartz formula 2009 or The Japanese Society for Pediatric Nephrology formula for patients in Japan).

In the case of any of the aforementioned laboratory abnormalities, the tests may be repeated once during screening and values resulting from repeat testing may be accepted for enrollment eligibility if they meet the eligibility criterion.

[43] Screening laboratory test values, including TSH, outside the reference range for the population or investigative site that, in the opinion of the investigator, pose an unacceptable risk for the patient's participation in the study.

Prior/Concurrent Clinical Study Experience

[44] Currently enrolled in any other clinical study involving an investigational product or any other type of medical research judged not to be scientifically or medically compatible with this study.

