7.4. Dosage Modification

The baricitinib dose for an individual patient will not change during the course of this study. However, the baricitinib dose for an age-based cohort may change based on the PK and safety profile of doses evaluated during the PK lead-in period. All patients who complete the PK lead-in period will enter the OLLI period on the dose they received at the start of the PK lead-in period. If the dose is modified for an age group after patients have already entered the OLLI period, they will be discontinued from the study and will be given the option to move to a separate OLE and receive the modified dose. Data from these patients will be censored from statistical analyses of efficacy endpoints in the present study.

The baricitinib dose for patients will be reduced by 50% in those who have renal impairment (defined as eGFR <60 mL/min/1.73 m²) at baseline. Patients receiving the 1-mg tablet who have renal impairment at baseline will be dose-reduced to 0.5-mg using the oral suspension.

Patients with eGFR <60 mL/min/1.73 m² are excluded from the safety/PK assessment period as described in Section 6.2.

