8.1. Discontinuation from Study Treatment

8.1.1. Temporary Interruption of Investigational Product

In some circumstances, patients may need to temporarily interrupt treatment as a result of AEs or abnormal laboratory values that may have an unclear relationship to investigational product. Except in cases of emergency, it is recommended that the investigator consult with Lilly (or its designee) before temporarily interrupting therapy for reasons other than those defined in [Table JAHV.7](#).

For the abnormal laboratory findings and clinical events (regardless of relatedness) listed in [Table JAHV.7](#), specific guidance is provided for temporarily interrupting treatment and when treatment may be restarted. Retest frequency and timing of follow-up laboratory tests to monitor the abnormal finding is at the discretion of the investigator. Investigational product that was temporarily interrupted because of an AE or abnormal laboratory value not specifically covered in [Table JAHV.7](#) may be restarted at the discretion of the investigator.

Table JAHV.7. Criteria for Temporary Interruption of Investigational Product

Hold Investigational Product if the Following Laboratory Test Results or Clinical Events Occur:	Investigational Product May be Resumed When:
WBC count <2000 cells/ μ L ($<2.00 \times 10^3/\mu$ L or <2.00 billion/L)	WBC count ≥ 3000 cells/ μ L ($\geq 3.00 \times 10^3/\mu$ L or ≥ 3.00 billion/L)
ANC <1000 cells/ μ L ($<1.00 \times 10^3/\mu$ L or <1.00 billion/L)	ANC ≥ 1500 cells/ μ L ($\geq 1.50 \times 10^3/\mu$ L or ≥ 1.50 billion/L)
Lymphocyte count <500 cells/ μ L ($<0.50 \times 10^3/\mu$ L or <0.50 billion/L)	Lymphocyte count ≥ 1000 cells/ μ L ($\geq 1.00 \times 10^3/\mu$ L or ≥ 1.00 billion/L)
Platelet count <75,000/ μ L ($<75 \times 10^3/\mu$ L or <75 billion/L)	Platelet count $\geq 100,000/\mu$ L ($\geq 100 \times 10^3/\mu$ L or ≥ 100 billion/L)
eGFR <40 mL/min/1.73 m ² (from serum creatinine) for patients with screening eGFR ≥ 60 mL/min/1.73 m ²	eGFR ≥ 50 mL/min/1.73 m ²
eGFR <30 mL/min/1.73 m ² (from serum creatinine) for patients with screening eGFR ≥ 40 to <60 mL/min/1.73 m ²	eGFR ≥ 40 mL/min/1.73 m ²
ALT or AST >5 x ULN	ALT and AST return to <2 x ULN, and IP is not considered to be the cause of enzyme elevation
Hemoglobin <8 g/dL (<80.0 g/L)	Hemoglobin ≥ 10 g/dL (≥ 100.0 g/L)
Symptomatic herpes zoster	All skin lesions have crusted and are resolving

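### SAP 6.18.5.4 measures renal effects only by creatinine grades, so no table in the SAP counts the children who met the protocol's eGFR interruption limits

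*SAP*

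**What the plan says.** SAP 6.18.5.4 (Renal Function Effects) names one measure: "Effects on renal function will be assessed through analysis of elevated creatinine". Table JAHV.6.19 gives two displays. One is a shift table from the most extreme baseline CTCAE grade to the maximum. The other counts treatment-emergent shifts "based on any increase to CTCAE Grade 1 or above, Grade 2 or above, Grade 3 or above, and Grade 4 or above". The section adds that the summaries "are described more fully in compound-level safety standards". eGFR is not mentioned.

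The protocol writes its renal rules in eGFR (mL/min/1.73 m²):

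- **Study entry (6.2):** patients with "eGFR < 40 mL/min/1.73 m² are excluded from enrolling in the study".
- **Safety/PK entry (6.2):** patients with "eGFR < 60 mL/min/1.73 m² are excluded from the Safety/PK period of the study".
- **Dose (7.4):** "The baricitinib dose for patients will be reduced by 50% in those who have renal impairment", defined as eGFR below 60 at baseline.
- **Temporary interruption (8.1.1, Table JAHV.7):** hold below 40 if screening eGFR was at least 60, resuming at 50 or more. Hold below 30 if screening eGFR was 40 to below 60, resuming at 40 or more.

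The footnotes to both schedules of activities say: "Clinical chemistry will include eGFR". In Table JAHV.2, clinical chemistry is scheduled at screening and at each visit from baseline to follow-up. Protocol Appendix 2 lists eGFR among the chemistry analytes.

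**The concern.** The protocol acts on eGFR and the SAP's renal topic reports creatinine. A reader of the study report would want to know how many children on baricitinib, and how many on placebo, fell to the level at which the protocol holds treatment. That count is the direct link between the renal rule and the renal safety result, and the renal section does not produce it.

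The mismatch stands out among the laboratory criteria in Table JAHV.7. White cells, neutrophils, lymphocytes, platelets and hemoglobin are analysed in SAP 6.18.5.2, and ALT and AST in 6.18.5.1. eGFR is the only laboratory criterion in that table whose matching SAP topic analyses a different variable.

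At stake is the completeness of the safety report. Temporary interruption of investigational product is also a listed safety endpoint, and the share of it triggered by eGFR would not be identifiable from the planned tables.

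**Working it through.** The plan states no figure to reproduce here. The check asks whether any SAP display could count patients meeting the Table JAHV.7 eGFR limits, and then whether creatinine grades could stand in.

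**Step 1. Displays that might carry the count**

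| Place | What it gives | Counts at the eGFR hold limits? |
|---|---|---|
| SAP 6.18.5.4, Table JAHV.6.19 | Creatinine CTCAE shifts | No |
| SAP 6.18.3, Table JAHV.6.12 | Box plots, treatment-emergent low/high, listing of abnormal values | Not specified; low/high means shifts out of normal |
| SAP 6.7, Table JAHV.6.2 | Screening eGFR below 60 versus 60 or more | No; not post-baseline |
| SAP 6.18.2, Table JAHV.6.11 | Interruptions due to an adverse event, by preferred term | No |
| Protocol 10.3.4.2 | Descriptive summary of all laboratory results; chemistry as change from baseline | No |

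The interruption table does not fill the gap. Protocol 8.1.1 allows a hold for an abnormal laboratory value as well as for an adverse event. Protocol 9.4.3 makes a laboratory finding reportable as an adverse event when it is clinically significant and results in a diagnosis. A hold triggered by eGFR alone need not appear there.

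**Step 2. Can creatinine grades be converted?**

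The documents name the eGFR formulas without giving them. Assume that eGFR is proportional to height divided by serum creatinine. At fixed height, the creatinine multiple that takes a child from starting eGFR E to limit L is

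multiple = E / L.

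| Screening stratum | Start E | Limit L | Multiple |
|---|---|---|---|
| 60 or more | 60 | 40 | 60/40 = 1.5 |
| 60 or more | 90 | 40 | 90/40 = 2.25 |
| 60 or more | 120 | 40 | 120/40 = 3.0 |
| 40 to below 60 | 40 | 30 | 40/30 = 1.33 |
| 40 to below 60 | just under 60 | 30 | just under 60/30 = 2.0 |

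A doubling of creatinine takes a child from 60 to 30, which meets the hold limit, and another from 120 to 60, which does not. If the grades are multiples of the child's own baseline, one grade covers both. If they are multiples of an upper limit, two children of different height with the same creatinine have different eGFR. Either way, the number of children at a given grade does not determine the number below 40 or 30.

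**Step 3. Which eGFR counts match the rule?**

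The limit depends on the screening stratum. A child screened at 42 who falls to 38 is below 40 but has not met the hold limit of 30. Flat counts below 60, 40 and 30 would therefore not reproduce the rule, and stratum-specific counts are needed.

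**The case against.** The strongest reply is that eGFR is not left out of the analysis. It is a listed chemistry analyte, so Protocol 10.3.4.2 and SAP 6.18.3 cover it with change from baseline, box plots, treatment-emergent low counts and a listing of abnormal values. SAP 6.18.5 also allows patient profiles where summary data are insufficient. This stands, and it confines the point to the special topic and to the missing count at the protocol's limits.

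Second, the detail may lie elsewhere. SAP 6.18 and 6.18.5.4 both refer to compound-level safety standards, which are not among the documents and may contain eGFR tables. This also stands, and the fix allows for it.

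Third, the hematology topic also uses CTCAE grades, so the lack of counts at hold limits is not peculiar to the kidney. That is true. The hematology topic does, however, grade the variables on which the hold rules are written.

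Two stronger readings are tempting, and the documents support neither:

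- **A hold-level loss would be invisible in the creatinine table.** The CTCAE version and its creatinine cut-offs are not given, so this cannot be tested. A child starting at half an upper limit with eGFR 100 reaches eGFR 50 when creatinine doubles, which is not a hold. Reaching 40 takes a multiple of 100/40 = 2.5, which puts creatinine at 0.5 × 2.5 = 1.25 times that limit. From half the limit, a hold-level loss stays within it only if starting eGFR is below 80, since half of 80 is 40. Nothing in the documents says how common that is.
- **Growth distorts the creatinine grades.** Under the same assumption, a height gain of 3% to 6% moves eGFR by 3% to 6%, small beside multiples of 1.33 to 3. In the double-blind period the arms are randomized, so growth should be similar on average.

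**Conclusion.** The point holds in limited form. The renal topic analyses creatinine grades alone, the protocol's renal rules are in eGFR, and no table described in the SAP counts patients who met the Table JAHV.7 eGFR limits. That creatinine grades cannot be converted into such a count rests on the assumed inverse relation between eGFR and creatinine. The textual mismatch does not depend on it.

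The number of children affected cannot be estimated from the documents. The importance is minor: this is a reporting gap in one safety topic, with no bearing on the time-to-flare analysis. The conclusion covers only the two documents and would fall away if the compound-level standards already specify these eGFR tables.

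**What to change.** In SAP 6.18.5.4, add eGFR as a renal measure, by treatment period and, in the double-blind period, by arm:

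1. Lowest post-baseline eGFR.
2. Number (%) below the existing Table JAHV.7 limit for the patient's screening stratum: below 40 if screening eGFR was at least 60, below 30 if it was 40 to below 60.
3. A shift table from screening eGFR category (at least 60; 40 to below 60) to lowest post-baseline category.
4. A listing of interruptions triggered by eGFR.
5. The number of patients with no post-baseline eGFR.

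Keep the creatinine CTCAE grades as supportive. If the compound-level safety standards already contain these displays, cite them in 6.18.5.4 instead.

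The cost is one table and one listing from data that the schedule already collects. Values may be missing for patients handled under Protocol Appendix 8. Its minimum local laboratory list has neither creatinine nor eGFR, yet it says the results let investigators follow the interruption criteria. That passage and Table JAHV.7 must be reconciled. Item 5 shows how far any missing values limit the counts.
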